H1: Older adults randomized to volunteering (vs. control) will report lower loneliness (H1a; UCLA Loneliness Scale)²⁷ and greater quality of life (H1b; WHOQOL Scale)²⁸ at 3, 6, 9, and 12 months.

Aim 2: *To examine increased social engagement, perceived usefulness, and perceived social support as mechanisms for reducing loneliness.*

H2: Older adults randomized to volunteering (vs. control) will report greater social engagement (H2a), perceived usefulness (H2b), and perceived social support (H2c) at 6 months, which will account for the effects on reduced loneliness at 12 months.

Aim 3: *To examine conditions under which volunteering is most effective at reducing loneliness.*

H3: The effect of volunteering vs. control on loneliness will increase with greater quantity (H3a; hours per month) and satisfaction (H3b).

H4 (exploratory): Given that functional impairment impacts all proposed mechanisms, the effect of volunteering vs. control on loneliness will be strongest for those with less functional impairment at baseline.

IMPACT: *National infrastructure for volunteering programs for older adults—The Senior Corps—ensures that volunteering is **highly scalable**. Dissemination and scaling up efforts will involve connecting primary care patients and aging services clients who are lonely with The Senior Corps, which we have shown to be feasible in our companion study, The Senior Connection. Existing infrastructure will make it possible to engage a large proportion of lonely older adults in volunteering, thereby reducing loneliness, improving well-being, and promoting health.*

II. CHARACTERISTICS OF THE RESEARCH POPULATION

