
g) Analytic Procedures:

Power analysis is conducted to test treatment effects by the intent-to-treat (ITT) analysis for the primary hypothesis. We assume a conservative 20% attrition rate and a 0.3 within-subject correlation. A sample size of N = 300 (or N = 150 per treatment group) will allow us to detect a small effect size of 0.2 for loneliness, with 80% power based on a two-sided type I alpha = 0.05. The assumed within-subject correlation of 0.3 reflects the relatively long time lag between consecutive assessments. The proposed sample size also has 80% power to detect 32% mediation effects for loneliness, a continuous outcome. If full mediation is not achieved for any of the mediators considered, 32% mediation effects are sufficiently large to be of clinical importance for the outcomes of interest.

Descriptive statistics will be computed to summarize distributions of each outcome, with means and standard deviations for continuous outcomes and percent for categorical outcomes. Two-sample t tests (or the Mann-Whitney-Wilcoxon rank sum test) and Chi-squares will be used to examine balance of treatment randomization for continuous (if distributions are highlight skewed) and categorical variables. The primary hypotheses are concerned about the effectiveness of volunteering on reducing loneliness vs. control. Examination of mechanisms (mediation, Aim 2) as well as dose-response relationships (Aim 3) and moderators (Aim 3) of the intervention will also be examined. Aim 1 (and Aim 3 H4 on moderation) will be tested using longitudinal regression models, while the mediation hypothesis (Aim 2) will be examined by structural equation models, and dose-response relationships (Aim 3) by structural mean models.

The two most popular longitudinal models are the generalized linear mixed-effect models (GLMM) and the weighted generalized estimating equations (WGEE). Weighting is based on inverse probability of drop-out, extending standard GEE from valid inference only under missing completely at random to missing at random, similar to GLMMs. For inference about treatment effects, both models can be applied. However, parametric

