The ITT analysis for Aim 1 provides intervention effects averaged over all subjects randomized to the intervention conditions. When intervention compliance (volunteering hours/satisfaction for subjects in the volunteering condition) demonstrates a dose-response relationship, as we hypothesize in Aim 3, complier average causal effects (CACE) are appropriate; thus we will use them to test Hypothesis 3. CACE is a compliment to ITT analyses and provides an answer to a different question than is answered by ITT analyses (i.e., the result of complying vs. being offered an intervention).⁷¹ CACE provides valid causal inference because it maintains randomization and includes all subjects in the analysis, as with ITT.⁷² CACE provides different intervention effects for individuals depending on their levels of compliance, which can be quite informative, especially when there is large variability in intervention compliance and strong dose-response relationships. The ITT and CACE estimates from a similar intervention study by Gruenewald, et al.⁷³ show that not only were the CACE effect sizes much larger than their ITT counterparts (small ITT vs. large CACE effect size), but the temporal trend also reversed; while the ITT effect sizes decreased, the CACE effect sizes increased from 4 months to 12 months post intervention, indicating substantial heterogeneity in intervention compliance and strong dose-response relationships. Since volunteering time is only required for the volunteering condition, standard statistical models cannot be used to perform CACE analysis. The CACE approach enables an estimate of the treatment effect at each level of "compliance" (i.e., amount of hours volunteered), without the need for a measure of compliance in the control group. In this way, we will be able to tell how well volunteering reduces loneliness at different "doses" of volunteering. The two most popular methods for addressing intervention compliance are the parametric principal stratification (PS) and the semi-parametric structural mean model (SMM).⁷⁴⁻⁷⁶ Unlike the PS, the SMM not only allows for continuous dose variables, but also requires no parametric model for data distribution such as normality, thereby yielding robust inference for a broader class of data distributions. We will use the latest SMM based on the structural functional response models (SFRM) for our CACE analysis, which not only allow for continuous, but also multiple dose variables.⁷⁴⁻⁷⁶ We are particularly interested in potential non-linear dose-response relationships so that we may determine optimal dose intervention whereby increased exposure (i.e., number of hours volunteered) becomes less worthwhile (in terms of reducing loneliness).

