
Aim 1 compares subjects randomized to either the volunteering or control on loneliness (continuous variable). **H1a:** There will be a condition effect on loneliness at all time points indicating differing levels of loneliness in the direction: control > volunteering. Longitudinal models will be employed with loneliness as the response, and condition, time and their interaction as the predictors, controlling for age, gender. If a significant difference exists (a significant time by condition interaction), appropriate linear contrasts will confirm the hypothesized directional effects. For **H1b**, the same analytic strategy will be used, but with quality of life (continuous) as the response variable. Aim 2 involves mediation analysis: is to examine perceived usefulness and social support as mediators of the intervention effect on loneliness. **H2a:** Increases in social engagement at 6 months is hypothesized to mediate the effect of intervention condition on decreased loneliness at 12 months. The SEM-based mediation models will be applied, with social engagement as the mediator, intervention condition as the predictor and loneliness as the outcome, controlling for age, gender. If the null of full mediation is rejected, we will estimate direct, indirect and total effects to assess the strength of mediation. The same analytic strategy

will be used for perceived usefulness and social support (**H2bc**). **Aim 3** involves when volunteering will provide maximal benefit. **H3:** Greater hours (compliance) and satisfaction will be associated with better outcomes. We will apply the SFRM-based SMM to analyze dose-response relationships. We will first model dose using non-parametric methods and then characterize the patterns using parametric methods. This allows us to capture detailed dose and response relationships and provide more interpretable findings. **H4:** The longitudinal model for H1a will be used with functional status as a moderator variable.

h) Data and Safety Monitoring Plan:

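### The stated 80% power for a loneliness effect of 0.2 is not reproduced from the plan's own inputs on a plain reading (about 61–78% without baseline adjustment), and the assumptions needed to check it are missing

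*Combined protocol and SAP*

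**What the plan says.** The power paragraph in III.g refers to the intent-to-treat test of the primary hypothesis. Its inputs are these: "We assume a conservative 20% attrition rate and a 0.3 within-subject correlation". With 150 per group the trial is said to be able to "detect a small effect size of 0.2 for loneliness, with 80% power based on a two-sided type I alpha = 0.05". The choice of correlation is explained as follows: "The assumed within-subject correlation of 0.3 reflects the relatively long time lag between consecutive assessments". The 2022 addendum raises the enrolment ceiling but keeps the target of 150 randomized per group.

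The analysis itself is described later in III.g. H1a reads: "There will be a condition effect on loneliness at all time points". H1 in Section I places the comparison "at 3, 6, 9, and 12 months". The longitudinal model has "condition, time and their interaction as the predictors, controlling for age, gender"; baseline loneliness is not among the listed covariates. The sequence of testing is then: "If a significant difference exists (a significant time by condition interaction), appropriate linear contrasts will confirm the hypothesized directional effects".

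**The concern.** This is the only sample-size justification for the primary hypothesis. Five things that determine power in a repeated-measures comparison are absent: the contrast, the correlation structure, the number of visits counted, the use of baseline, and when the 20% are lost. If the natural readings all gave about 80%, the omission would be cosmetic. They do not. On several of them a true 0.2 SD effect would be missed well over the planned 20% of the time, and someone interpreting a null result would credit the trial with more sensitivity than its inputs support.

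The first test named for H1a is also not obviously the test that was powered. A reader cannot tell whether the 80% refers to that test, to an average over visits, or to something else.

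**Working it through.** **Inputs from the plan (III.g):** 150 per arm, 20% attrition, correlation 0.3, effect 0.2, two-sided 5% level. Follow-up is at months 3, 6, 9 and 12 (Section I, H1).

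**Assumptions made here:** 0.2 is in SD units; the contrast is the average difference over the four follow-up visits; age and gender explain nothing, because the documents give no figure.

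**Method.** Power = Φ(0.2/SE − 1.96). For 80% the SE must be at most 0.2/2.802 = 0.0714.

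**Plain reading: all 20% lost before month 3, so 120 per arm.** Variance of a four-visit mean, in SD² units:
- Exchangeable: (1 + 3 × 0.3)/4 = 0.475. SE = √(2 × 0.475/120) = 0.0890. Power = Φ(2.248 − 1.96) = **61.3%**.
- AR(1): [4 + 2(3 × 0.3 + 2 × 0.09 + 0.027)]/16 = 0.388. SE = √(2 × 0.388/120) = 0.0805. Power = Φ(2.486 − 1.96) = **70.1%**.

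Neither gives 80%. With no attrition at all, exchangeable correlation gives SE = √(2 × 0.475/150) = 0.0796 and power 71.0%.

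**Adding baseline adjustment, same dropout.** Subtract the squared covariance of the four-visit mean with baseline:
- Exchangeable: 0.475 − 0.3² = 0.385; power 70.4%.
- AR(1): covariance (0.3 + 0.09 + 0.027 + 0.0081)/4 = 0.106; 0.388 − 0.106² = 0.377; power 71.3%.

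**Varying dropout timing.** Here information is summed over dropout patterns, using all partial data. Cells give power (%) for the efficiently weighted (GLS) common effect; figures in brackets weight the four visits equally. Gradual means 5% lost before each of the four visits.

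| Model | All before month 3 | Gradual | All after month 6 | All at month 12 |
|---|---|---|---|---|
| Exchangeable, unadjusted | 61.3 (61.3) | 66.7 (66.5) | 68.6 | 70.0 (69.8) |
| AR(1), unadjusted | 70.7 (70.1) | 75.2 (74.4) | 76.5 | 78.3 (77.9) |
| Exchangeable, baseline-adjusted | 70.4 (70.4) | 75.4 (75.2) | 77.1 | 78.7 (78.4) |
| AR(1), baseline-adjusted | 72.3 (71.3) | 76.8 (75.6) | 78.2 | 79.9 (79.1) |

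Four cells lie within 2 points of 80%: the last three rows with all loss at month 12, and the last row with all loss after month 6. All four need late loss, together with AR(1), baseline adjustment or both.

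**Effect detectable with 80% power (2.802 × SE, GLS), early / gradual / month-12 loss:**
- Exchangeable, unadjusted: 0.249 / 0.234 / 0.225 SD
- AR(1), unadjusted: 0.224 / 0.212 / 0.204 SD
- Exchangeable, baseline-adjusted: 0.224 / 0.212 / 0.203 SD
- AR(1), baseline-adjusted: 0.220 / 0.208 / 0.200 SD

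**The time-by-condition test.** This is a separate calculation: five visits, 4 degrees of freedom, and a constant 0.2 effect at every visit after baseline. With exchangeable correlation and no attrition the noncentrality is (150/2) × 0.2² × 4/(5 × 0.7) = 3.43, and power is about 28%. With 20% attrition and partial data kept, as intent-to-treat requires, power is 25.1–27.3% (exchangeable) or 20.8–22.3% (AR(1)). A constant 0.2 effect would therefore fail this test about 73–79% of the time.

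**The case against.** **The calculation may be under-described rather than wrong.** This stands. III.g names no contrast, and the months 3–12 average is supplied here. The sentence "The ITT analysis for Aim 1 provides intervention effects averaged over all subjects randomized to the intervention conditions" does not settle it, since it speaks of averaging over subjects, not over visits. A reader might infer a demonstrated slip by the sponsor; the documents do not show one. They show that the figure does not follow from the inputs given.

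**The effect is quoted to one decimal.** Detectable effects of 0.20 to 0.25 SD all print as 0.2 (the largest is 0.249). This is fair as a measure of how small the gap can be. It does not rescue the statement, which attaches 80% to 0.2 itself.

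**AR(1) is a reasonable reading.** The plan ties 0.3 to the lag between consecutive assessments, so AR(1) fits at least as well as exchangeable correlation. The 61% figure is the harshest corner of the table, and the AR(1) rows deserve equal weight.

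**80% can be reached.** A reader might infer that it needs AR(1), baseline adjustment and all loss at month 12 together. That is too strong: three other late-loss cells reach 78.2–78.7%. Unadjusted AR(1) also gives 80.0% if attrition is ignored, though that drops a stated input. Counting baseline as a fifth outcome under AR(1) gives about 80–86%, but it averages a treatment effect over a pre-randomization value, which is not sound.

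**Age and gender are in the model.** If they explained enough variance, power would rise. The share needed, 1 − (0.2/2.802)²/SE², is 0.4–4% in the month-12 column for the last three rows. It is 21–36% across dropout timings for exchangeable unadjusted. The documents give no figure.

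**The interaction test is a different matter.** III.g claims no power for it, so its low power does not contradict the 80%. It matters only if that test is a true gate.

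**Conclusion.** The point holds as a correctable shortfall in the power statement. With the stated attrition, and without a baseline covariate as the model is listed, power at 0.2 SD is about 61–70% (exchangeable) or 70–78% (AR(1)). The effect would thus be missed 30–39% or 22–30% of the time, against the stated 20%. With baseline adjustment, power is 70–79% or 71–80%. Gradual loss gives at most 77%.

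These figures rest on SD units, the months 3–12 average, and no contribution from age and gender. On favourable readings the gap is a point or two of power.

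A reader might go further and infer that the trial is too small. The documents do not support that: at 80% power the detectable effect stays between 0.20 and 0.25 SD, and several defensible readings lie at the lower end.

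**What to change.** Restate the power paragraph for a named primary contrast. Give the visits counted, the correlation structure, the dropout timing, the handling of baseline loneliness and the unit of the effect size. Then report either the matching power at 0.20 or the effect detectable with 80% power to two decimals. On the readings above, the latter is about 0.23–0.25 SD for exchangeable correlation without baseline adjustment, and about 0.20–0.22 SD under AR(1) or with baseline adjustment.

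If the time-by-condition test stays as the first step, report its own power.

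The cost is rewording one paragraph. Enrolment does not change, and the only downside is a less favourable stated figure.

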Montreal Cognitive Assessment (MOCA) ³⁸	Global cognitive functioning	The Montreal Cognitive Assessment (MoCA) was designed as a rapid screening instrument for mild cognitive dysfunction. It assesses different cognitive domains: attention and concentration, executive functions, memory, language, visuoconstructional skills, conceptual thinking, calculations, and orientation. Time to administer the MoCA is approximately 10 minutes. The total possible score is 30 points; a score of 26 or above is considered normal. Nasreddine and colleagues report high sensitivity and specificity for MOCA scores in detecting MCI. ³⁸ The MOCA has three alternate forms in English to prevent practice effects with repeat administration, as well as a form for blind individuals.	10 – 15 minutes at baseline and final interview (alternate form used at final interview)
Columbia Suicide Severity Rating Scale (CSSRS) ³⁹	History of suicidal ideation and behaviors	The CSSRS is an interview that assesses for worst-point lifetime and past month suicidal ideation and behavior. It has been shown to predict future suicidal behavior ³⁹ and is the current gold standard for assessing suicide risk in clinical trials.	5 –15 minutes In-person interviews (time frame is “since last visit” for follow-up interviews)
Mood Improvement Protocol (MIP)	Self-perceived distress (before and after interview) and coping strategy (i.e., mood improvement activity)	The research interview may elicit negative reactions in individuals who are having difficulties in areas of their life related to questions in the assessment. Thus, this measure, adapted from procedures designed by Linehan and colleagues, is designed to enhance retention and improve subjects' experience in the research assessments.	5 – 10 minutes In-person interviews
Qualitative Feedback	Subject's experience in the research program	Open-ended questions to assess the subject's experience throughout the research program	5-10 minutes 6 and 12 month interviews
Volunteer Satisfaction Survey and Volunteer Benefits Survey	Subject's experiences in the volunteer program	Feedback to assess the subject's satisfaction and benefits from volunteering	5 minutes Volunteer condition only 6 month and final interview
Life Review Satisfaction Survey	Subject's experiences in the life review program	Feedback to assess the subject's satisfaction with life review	2 minutes Life Review condition only 6 month and final interview

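### H3b uses satisfaction as a compliance dose in the CACE model, which cannot support a causal claim about satisfaction and, in its simplest form, only re-tests the ITT effect

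*Combined protocol and SAP*

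**What the plan says.** - Specific Aims, H3: "The effect of volunteering vs. control on loneliness will increase with greater quantity (H3a; hours per month) and satisfaction (H3b").
- III.g Analytic Procedures, CACE paragraph: "When intervention compliance (volunteering hours/satisfaction for subjects in the volunteering condition) demonstrates a dose-response relationship", the plan holds that "complier average causal effects (CACE) are appropriate; thus we will use them to test Hypothesis 3". It adds that CACE inference is causally valid because randomisation is preserved and everyone is analysed. Effects by dose are to be estimated "without the need for a measure of compliance in the control group", with structural mean models (SMM) built on structural functional response models (SFRM), "which not only allow for continuous, but also multiple dose variables". Where the paragraph explains what dose means, it mentions hours only.
- III.g, Aim 3: "We will apply the SFRM-based SMM to analyze dose-response relationships". Dose is modelled non-parametrically first and parametrically afterwards. No intercept, origin, tested parameter or identifying covariate is given.
- III.e, Volunteer Satisfaction Survey: the schedule reads "Volunteer condition only 6 month and final interview". The score range and anchors are not given. UCLA loneliness is measured at every visit, including those two.
- III.f, volunteering condition: hours come from monthly timesheets collected by the agency.

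**The concern.** A dose model that relies on randomisation needs two things: a dose level that means nothing was received, and an effect of assignment that acts through the dose. Hours can meet both at least plausibly, since a subject with zero hours has had no volunteering.

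Satisfaction, as described, does not. It is an opinion formed after exposure and has no meaning for controls. It is equally undefined for an assignee who never volunteered, for example one who fails the background check that follows randomisation (III.d), if kept in the ITT set. Such a subject has zero hours but no satisfaction score. And a subject who volunteers every week and dislikes it has still received the intervention, so the whole effect of assignment cannot be assumed to run through satisfaction. Randomisation does not repair this, because satisfaction was not randomised.

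At stake is a named hypothesis reported with a causal label. A reader could be told that raising satisfaction lowers loneliness when the data show only that volunteering does.

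**Working it through.** **1. The plan's own power figure.** III.g gives 150 per arm, effect 0.2 SD, 20% attrition, within-subject correlation 0.3, two-sided alpha 0.05 and 80% power. No power is stated for H3b. Assume four follow-up visits, equal correlation between visits, and the mean over visits as outcome:
- completers per arm: 150 × 0.8 = 120
- variance of the mean: (1 + 3 × 0.3)/4 = 0.475
- standard error of the difference: √(2 × 0.475/120) = 0.0890
- power: Φ(0.2/0.0890 − 1.96) ≈ 61%

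Baseline adjustment (variance 0.475 − 0.3² = 0.385) gives 70%. The 80% is not reproduced by either. It appears under other choices, such as baseline adjustment with attrition ignored (79.7%), or five visits with first-order autoregressive correlation and about 131 per arm (81%). The point here does not depend on which was used.

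**2. One slope through zero.** Let the effect for a volunteer with satisfaction S be ψS, with S set to 0 in controls. Then

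mean(Y, volunteering) − mean(Y, control) = ψ × mean(S, volunteering),

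so the estimate is ψ = ITT mean difference / mean satisfaction. For any positive mean, ψ is zero exactly when the ITT difference is zero, and its test is that ITT test rescaled. Illustration with an assumed 1–5 scale and mean 4: −0.2/4 = −0.05 SD per point, even if satisfaction does nothing.

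**3. Simulation.** 4,000 trials per setting, 120 per arm, outcome variance 0.475. The volunteering effect is the same for everyone, so satisfaction (assumed mean 4, SD 0.8) has no effect. Entries are the share of trials significant in the favourable direction; the nominal rate is 2.5%.

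| Volunteering effect (SD) | ITT mean difference | One slope through zero | Intercept plus tested slope |
|---|---|---|---|
| 0 | 2.6% | 2.5% | 2.2% |
| 0.2 | 62% | 62% | 2.2% |
| 0.3 | 92% | 92% | 2.3% |
| 0.5 | 100% | 100% | 2.4% |

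With mean satisfaction 3 and SD 1, the one-slope model gives 91% at 0.3 SD, against 92% for ITT. The last column keeps its error rate only because a baseline covariate correlated 0.5 with satisfaction was assumed, and its interaction with arm separates slope from intercept.

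**4. What two arms can identify.** At a given visit, two randomised arms supply one mean contrast, and that fixes one effect parameter. A separate slope, a curve or a second dose needs further information. The plan names none.

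**5. Timing, a separate matter.** With satisfaction tied to prognosis (correlation 0.3), the one-slope model still gives 2.5% at no volunteering effect, and 93% at 0.3 SD (ITT 92%). So measurement at the same visit does not cause the result in step 2. It does affect an association within the volunteering arm. With satisfaction tied to prognosis, that association was significant in 86–87% of trials, even with no volunteering effect. It was significant in 36–37% when individual response drove satisfaction. These rates show how large the problem can be; they do not measure what would remain after the adjustment proposed under the fix.

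**The case against.** The strongest defence is that the plan does not commit to one slope through zero. It plans non-parametric modelling first, allows several doses and is interested in non-linear relationships, and a model with its own intercept and slope holds its error rate. This stands. A reader might infer that H3b must come out positive whenever volunteering works; the documents do not support that, because the functional form is open. The defence does not remove the problem, since the form that is safe needs an intercept, a tested slope and an identifying assumption, and none of them is in the plan.

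Other points that stand:
- A reader might equate rejection of H3b with rejection of H1a. H1a is tested by a time-by-condition interaction followed by contrasts, whereas the one-slope test matches a mean-difference ITT test. The 62% therefore belongs to the latter.
- A reader might take it as documented that the satisfaction scale lacks a zero. The scale is not given. The argument rests on when and from whom the score is collected, not on its anchors.
- A reader might blame same-visit measurement for the link to the ITT test. Step 5 shows otherwise. Six-month satisfaction could be paired with 12-month loneliness, but no pairing is stated.
- Hours in a one-slope model would track the ITT test as well, though for hours the assumption of no effect at zero dose is meaningful.
- III.g words H3 in the Aim 3 paragraph as an association, and H3 is not the primary hypothesis.

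**Conclusion.** The concern holds in this form: satisfaction is planned as a compliance dose under a claim of causal validity, and the analysis as written cannot support that claim. This is more than missing detail, because the written design supplies nothing that would separate a satisfaction effect from the overall effect of assignment.

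The size is conditional. In the one-slope form, a satisfaction effect that does not exist would be declared in about 62% of trials at 0.2 SD and 92% at 0.3 SD, assuming 120 completers per arm, the mean of four visits, correlation 0.3 and a volunteering effect equal for all. The satisfaction scale and effects above 0.2 SD are assumptions, though the algebra holds for any positive mean score. In the intercept-and-slope form the rate is nominal, given an identifying covariate. The unstated pairing of visits adds a separate risk that loneliness drives satisfaction. The primary ITT comparison is not affected.

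**What to change.** 1. Take satisfaction out of the compliance (CACE) dose and keep study volunteering hours as the dose. Test H3a on a dose-response slope or curve rather than on a single ratio parameter, and state the assumption that identifies it.
2. Report H3b as an explicitly non-causal association within the volunteering arm: 6-month satisfaction predicting 12-month loneliness, adjusted for baseline and 6-month loneliness, age, gender and hours. Define the satisfaction score.
3. If H3b is to be compared with control, prespecify a slope in satisfaction separate from the overall effect, with its identifying assumption and a rule for assignees who never volunteered.

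The cost is SAP wording; the data are already scheduled for collection. H3b loses its causal label. The association within the arm can still reflect prognosis, does not use the control arm, and sets aside benefit already reached by 6 months because 6-month loneliness is adjusted for. The report should say so.
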